vaccination. Prior studies demonstrate <15% of pregnant women received any doses of HPV vaccine and <8% completed the series.¹⁵⁻¹⁸ Given this window of opportunity, a few investigators have implemented postpartum HPV vaccination at their institutions, and the Departments of Health in the states of New York and Washington recommend it for women who have not completed the series.^{18,19} One of the first postpartum HPV vaccination studies enrolled a sample of 150 Hispanic women who tolerated the vaccination with few side effects and patients reported a high degree of satisfaction.²⁰ However, 30% of the women completed all 3 doses, 23% received two doses, and 41% received only one dose during hospitalization. Completion of the series of three HPV doses was a challenge. The second study, also done in Texas, used patient navigators who used multiple reminder methods (texting, mailed reminders, and phone calls) to increase completion rates. This study reported a 65% completion rate and 75% of postpartum women received at least one dose.²¹ Future studies should determine the optimal method to ensure vaccine series completion while using minimal resources and existing staffing.

Two Dose Regimen for HPV Vaccination

A two-dose regimen includes administration of an inactivated vaccine with the first dose as the priming dose and the second distant dose resulting in consolidation of the immune response.²² The second dose administered at 6-months to allow complete initial B cell response stimulation; affinity-matured B cells produce an amnestic response after booster, but affinity maturation takes at least four months to develop. Recent studies have demonstrated non-inferiority of HPV vaccination in a two-dose regimen in adolescents.²² A two-dose regimen may be beneficial in older patients as well, especially those who have difficulty with follow up for multiple doses of a vaccine regimen, but this has not been studied.

4. Study Procedures

a. Study design, including the sequence and timing of study procedures Pilot, non-inferiority clinical trial using historical controls

Participants will have whole blood drawn at 0-months, 6- to 12-months, and one month after the second dose of the vaccine. The HPV vaccine will be administered at 0-months, 6- to 12-months, and two to five months after the second dose of the vaccine. Each blood draw will consist of 15 mL to measure HPV serologies and hormone levels.

Initial contact

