- After the baseline visit (0-months), all follow-up visits will take place at an OB/GYN clinic or a CRU located at Johns Hopkins Hospital or Bayview.
- Participants will be contacted by the research team at 5-months using their preferred contact preference to schedule a 6-month research visit at an OB/GYN clinic or a CRU.
- If participants cannot come at 6-month for the second visit, the research team will contact them to schedule a research visit between 6 and 12 months.
- Participants will be asked for their last menstrual period date and provide 20mL of urine for a pregnancy test before proceeding with the study.
- If the pregnancy test is negative, participants will have 15mL of blood drawn and labelled with a unique study ID.
- A vial of the vaccine will be ordered from the Pharmacy and Investigational Drug Services (IDS) through EPIC and dose #2 will be administered by a licensed medical provider per clinical protocol (e.g., intramuscular [deltoid]).
- After the vaccine is administered, the study coordinator will observe the participant for 15 minutes to note any untoward events or allergic reactions.
- Participants will be scheduled for their visit 3.
- If the pregnancy test is positive, participants will be withdrawn from the study. Participants will be advised to contact their OB/GYN for further clinical management.

Visit 3 (One month after Visit 2)

- Participants will have their final blood draw of 15mL collected and labelled with a unique study ID.
- There is no vaccine administered at this visit.

Visit 4 (One to five months after Visit 3)

- At Visit 3, participants will be scheduled for a study visit during in one to six months that will take place at an OB/GYN clinic or a CRU located at Johns Hopkins Hospital or Bayview. This is the time for a routine gyn annual examination, and the vaccine can be administered during that visit as well.
- Participants will be asked for their last menstrual period date and to provide 20mL of urine for a pregnancy test before they can precede with the final vaccine dose.
- A vial of the vaccine will be ordered from the Pharmacy and Investigational Drug Services (IDS) through EPIC and dose #3 will be administered by a licensed medical provider per clinical protocol (e.g., intramuscular [deltoid]).

- After the vaccine is administered, the study coordinator will observe the participant for 15 minutes to note any untoward events or allergic reactions.
- There is no blood drawn at this visit.

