Participants biologically born as females between the ages of 15 through 45 who are willing to have the HPV vaccine at the hospital after delivering a live born baby.

Exclusion Criteria

Severe allergic reaction to vaccine components, prior receipt of an HPV vaccine dose, fetal demise or stillbirth, allergy to yeast, moderate or severe acute illness (deemed by the investigator to exclude), and immunosuppression (e.g., HIV, solid organ transplant).

6. Drugs/ Substances/ Devices

a. The rationale for choosing the drug and dose or for choosing the device to be used. GARDASIL 9 is an inactive HPV vaccine that is administered intramuscularly and available in 0.5mL single does vials. GARDASIL 9 is commercially approved by the FDA for the prevention of cervical, vulvar, vaginal, and anal cancer caused by HPV types 16, 18, 31, 33, 45, 52, and 58. Participants will receive the recommended FDA dosage throughout the course of the study.

b. Justification and safety information if FDA approved drugs will be administered for non-FDA approved indications or if doses or routes of administration or participant populations are changed.

Gardasil-9 is FDA approved as a 3-dose series for patients 15-45 years old, and as a 2-dose series for patients 9-14 years old. In a 3-dose series, the second dose is usually given 1–2 months after the first dose, and the third dose is usually given 6 months after the first dose (0, 1–2, 6 month schedule). Per the Centers for Disease Control and Prevention, there are minimal intervals for administration of the HPV vaccine but no maximum intervals.²³ The minimum intervals are 4 weeks between the first and second dose, 12 weeks between the second and third doses, and 5 months between the first and third doses. If a vaccine dose is administered after a shorter interval, it should be re-administered after another minimum interval has elapsed since the most recent dose. If the vaccination schedule is interrupted, vaccine doses do not need to be repeated (no maximum interval). To stay in compliance, all participants will still receive 3 doses of the vaccine, although the scheduling is different. We are allowing enough time between doses (minimal interval) to allow an appropriate B-cell response and participants will complete the series within one-year. Therefore, this study aligns with the lack of a maximum interval and poses no change in risk compared to the traditional dosing schedule.

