c. Justification and safety information if non-FDA approved drugs without an IND will be administered.

N/A

7. Study Statistics

- a. Primary outcome variable.
 - Anti-HPV16 antibody titers measured four weeks after the second dose.

b. Secondary outcome variables.

- Antibody titers to the other 8 HPV types
- Seropositivity for each HPV type after 1-dose and 2-doses
- Percentage of participants who complete 1-dose, 2-dose, or 3-dose vaccination
- Percentage of participants with baseline titers suggestive of natural infection or prior vaccination
- Characteristics and percentage of participants who completed study visits in-person using their own transportation, required Lyft, or requested a home-visit. Characteristics will include individual demographic characteristics, sexual reproductive health history, STI history, neighborhood median income based on zipcode and neigborhood deprivation index based on address.
- Thematic coding of field notes if home visits were conducted

c. Statistical plan including sample size justification and interim data analysis.

Geometric mean titer (GMT) ratios for each HPV genotype will be compared between the 2dose and 3-dose regimen. As a non-inferiority trial, the primary analysis will use the perprotocol analysis. One-sided 90% confidence intervals (adjusted for multiple comparisons) will be constructed for the primary immunogenicity, which is the accepted method of reporting noninferiority results. Antibody GMTs at month-7 (4 weeks after 2nd dose) among participants who received the 2-dose regimen will be compared with historical controls who received the 3-dose regimen.²⁴ The criteria for declaring non-inferiority will be defined as the lower bounds of the multiplicity-adjusted 90% CI for the ratio of antibody GMT greater than 0.67. This noninferiority margin was selected based on bridging studies used for licensure.²⁵

Table 1: Statistical Intervals²⁶

Confidence	Sample	Actual Distance	Standard
Level	Size (N)	from Mean to Limit	Deviation (S)

0.900	107	0.125	1.000
0.900	107	0.150	1.200

Estimating the standard deviation of the GMT ratio to be 1.2 based on preliminary data, a sample size of 107 will produce a one-sided 90% confidence limit with a distance from the mean to the limit of 0.15. That is, if the GMT mean ratio is \geq 0.82, we will be 90% confident that the true ratio is not less than 0.67. To allow for almost 28% attrition, we will enroll 231 subjects.

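### A woman who misses Visit 3 but attends Visit 4 receives dose 3 unsampled; a conditional pre-vaccine draw at Visit 4 would keep her two-dose serology at little cost (minor)

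*Combined protocol and SAP*

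**What the plan says.** All references are to the combined protocol and SAP.

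- **Section 4a, Visit 3** ("Visit 3 (One month after Visit 2"): no vaccine is given. "Participants will have their final blood draw of 15mL collected and labelled with a unique study ID". No visit window is stated.
- **Section 4a, Visit 4** ("Visit 4 (One to five months after Visit 3"): dose 3 is given. "There is no blood drawn at this visit". The written booking step is: "At Visit 3, participants will be scheduled for a study visit during in one to six months". The visit may coincide with a routine annual gynaecology examination.
- **Section 4a, design summary**: three draws are listed, the last one month after dose 2. Dose 3 is timed as "two to five months after the second dose of the vaccine", that is, from dose 2 and not from Visit 3.
- **Section 4a, Visit 2**: a woman who cannot come at 6 months is re-contacted and rebooked up to 12 months. No such rule is written for Visit 3 or Visit 4.
- **Section 4a, Home visits**: available for Visits 2 to 4, with a nurse able to draw blood and inject, following the same visit procedures.
- **Section 6b**: "To stay in compliance, all participants will still receive 3 doses of the vaccine, although the scheduling is different".
- **Section 7a**: the primary outcome is the anti-HPV16 titer four weeks after dose 2.
- **Section 7b**: a secondary outcome is "Seropositivity for each HPV type after 1-dose and 2-doses", with no four-week limit attached.
- **Section 7c**: the primary analysis is per-protocol. No rule is given for a missing post-dose-2 sample.

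**The concern.** The trial asks what two doses achieve. A woman at Visit 4 who missed Visit 3 has had exactly two doses and is present in person, in a clinic or with a nurse at home. The procedure as written vaccinates her without taking blood. Once dose 3 is given, no later sample can show her two-dose response.

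She then drops out of 2-dose seropositivity for all nine types. The loss is avoidable and may be selective: women who miss a visit could differ in access and social circumstances from those who keep every visit. The plan itself treats access as relevant, since section 7b records transport, home visits and neighbourhood deprivation.

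**Working it through.** **1. Can a woman reach Visit 4 without a Visit 3 sample?** Yes.

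- Section 4g removes women for severe adverse events or pregnancy, not for a missed visit. Withdrawal for non-compliance in section 7d is at the investigator's discretion.
- Section 6b keeps her due for dose 3, and the design summary times that dose from dose 2.
- Visit 4 can fall on a routine annual examination. Visit 3 has no such link to routine care.

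**2. What would a Visit 4 sample measure?** Visit 3 is one month after dose 2. By its heading, Visit 4 is 1 to 5 months later, so about 2 to 6 months after dose 2. A draw there is not the four-week titer. Taken before the vaccine, it is still a sample after two doses and fits the wording of the secondary seropositivity outcome.

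**3. The plan's own sample size (section 7c).** Inputs: SD 1.2, n = 107, one-sided 90%.

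- Distance = t(0.90, 106) × 1.2/√107 = 0.1496, which reproduces the stated 0.15. With SD 1.0 it is 0.1247, against 0.125 in Table 1.
- Enrolment of 231 with 28% attrition leaves 231 × 0.72 = 166. The 231 does not follow from 107 at that rate: 107/0.72 = 149, and 107 evaluable of 231 would mean 1 − 107/231 = 53.7% attrition. The 28% is therefore used below only as a rough scale.

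**4. How many samples might be recovered?** No missed-Visit-3 rate is given. Two assumptions are needed: all the 28% loss falls by Visit 3, and 10 to 30% of the lost women had dose 2, missed Visit 3 and later attend Visit 4.

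- Lost: 231 × 0.28 = 64.7, about 65.
- 10%: 64.7 × 0.10 = 6.5, about 6. 30%: 64.7 × 0.30 = 19.4, about 19.
- Relative to 166: 6/166 = 4% and 19/166 = 11%.

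**5. Is primary precision at risk?** Suppose a further 5 to 30% of the 166 miss Visit 3 (also assumed).

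- 231 × 0.72 × 0.95 = 158 women, distance 0.123.
- 231 × 0.72 × 0.70 = 116 women, distance 0.144.

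Both are within 0.15. If the same losses came off 107 itself (107 × 0.95 = 101.7 and 107 × 0.70 = 74.9, rounded down to 101 and 74), the distance would be 0.154 to 0.180. A Visit 4 draw would not repair that, because it does not supply the four-week titer.

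**6. Visit 4 timing statements side by side.**

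| Place | Statement | Implied time after dose 2 |
|---|---|---|
| 4a, Visit 4 heading | 1 to 5 months after Visit 3 | about 2 to 6 months |
| 4a, Visit 4 first bullet | booked at Visit 3, 1 to 6 months ahead | about 2 to 7 months |
| 4a, design summary | timed from dose 2 | 2 to 5 months |
| 6b | cited minimum between doses 2 and 3 | 12 weeks |

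These do not agree at the upper end, and two months is shorter than 12 weeks.

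**The case against.** **Visit 3 can be rescued.** Nothing forbids a rebooked or home Visit 3 draw before dose 3, and section 7c speaks of the success of home visits in keeping women in the study. This stands, and it narrows the affected group to women for whom rebooking was not done or failed. It does not close the gap: no section directs the rebooking, and a home Visit 4 follows the same no-blood procedure.

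**The four-week titer is lost anyway.** This also stands. The Visit 4 sentence does not cause the missed primary sample. It only removes the last chance to see two-dose seropositivity.

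**Few women may take this path.** Section 10 pays $50 and covers transport at Visit 3 and lists neither for Visit 4, so skipping Visit 3 and attending Visit 4 may be uncommon. Some of the 65 would also be lost before dose 2 or withdrawn for pregnancy, and a Visit 4 draw does nothing for them. This is why the count may be below 6.

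**A stronger reading.** A reader might infer that Visit 4 can be booked only at Visit 3, so that a woman who misses Visit 3 has no route to dose 3, in contradiction of section 6b. The text does not support this. The booking sentence describes the usual sequence and contains no such restriction. Dose 3 is not made conditional on Visit 3, the design summary times it from dose 2, and section 6b commits everyone to three doses.

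**Conclusion.** The point holds as a minor, cheap improvement. Visit 3 is the sole post-dose-2 draw, no rescheduling rule is written for it, and the Visit 4 procedure gives dose 3 to an unsampled woman, after which her two-dose serology cannot be recovered.

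The size is unknown. The range of 6 to 19 samples rests on two assumptions that the documents do not support with data: that the 28% loss falls by Visit 3, and that 10 to 30% of those women return for Visit 4. A reader might infer that the primary analysis is endangered. It is not endangered by this sentence: the four-week titer is untouched by what happens at Visit 4, and about 166 evaluable women already exceeds 107. The gain is confined to a descriptive secondary outcome and a supporting analysis that the plan does not yet contain.

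**What to change.** 1. **Visit 4 wording (section 4a).** State that no blood is drawn unless the Visit 3 sample was not obtained. In that case the planned 15 mL sample is drawn before any vaccine given at that visit, and its date is recorded. Visit 2 already lists the draw ahead of the injection.
2. **Analysis (section 7c).** Label these samples as off-time. Use them only for 2-dose seropositivity and a sensitivity analysis of geometric mean titers, and show results with and without them. Keep the primary analysis on the four-week draw.
3. **Reconcile.** The Visit 4 booking and timing statements must be brought into line with the section 4a design summary and section 6b. How is for the sponsor to decide.

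**Cost.** Protocol and consent wording must change, and off-time samples need a separate label. No woman exceeds the three planned draws, since this one replaces the missed Visit 3 draw, and the samples join the single shipment at study end.

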Research Justification

One of the main reasons the HPV vaccine has had such poor compliance is lack of access to care. Vulnerable women that would benefit most from the HPV vaccine are often otherwise healthy individuals with minimal interactions with the healthcare system. However, as most pregnant women receive some prenatal care, the postpartum period is ideal to educate and implement a HPV vaccination program. Prior studies demonstrate <15% of pregnant women had received any doses of HPV vaccine and <8% completed the series. Given this window of opportunity, a few investigators have implemented postpartum HPV vaccination at their institutions, and the Departments of Health in the states of New York and Washington recommend it for women who have not completed the series.

2. **Objectives** (include all primary and secondary objectives)

Our primary aim is to determine whether a two-dose 9-valent HPV vaccination regimen is non-inferior to a three-dose regimen. The first dose will be given after giving birth while inpatient.

3. Background (briefly describe pre-clinical and clinical data, current experience with procedures, drug or device, and any other relevant information to justify the research)

The human papillomavirus (HPV) is the most common sexually transmitted infection (STI) in the United States (U.S.) and is responsible for a wide range of conditions, including cancers within the anogenital tract and the oropharynx. Each year in the U.S., HPV causes approximately 330,000 cases of precancerous cervical dysplasia and 12,000 cases of cervical cancer, the most common cancer in women attributable to HPV.¹ In 2012, there were 249,512 prevalent cervical cancer cases and 4,092 deaths in the U.S. Although infection with HPV is extremely common and most women will become infected with HPV at some point in their lives, ² the majority of infections are asymptomatic. ^{3,4} However, if infection persists, over time, precancerous disease can eventually develop into cancer and spread through the body.

Prophylactic HPV Vaccine

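### Section 7c adjusts the HPV16 non-inferiority limit for multiplicity without saying over what, in conflict with the single primary outcome in 7a and with its own unadjusted precision statement

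*Combined protocol and SAP*

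**What the plan says.** Section 2 states the aim for the vaccine as a whole: "Our primary aim is to determine whether a two-dose 9-valent HPV vaccination regimen is non-inferior to a three-dose regimen". Section 7a has one primary outcome, "Anti-HPV16 antibody titers measured four weeks after the second dose", and 7b lists "Antibody titers to the other 8 HPV types" as secondary.

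Section 7c then covers all nine types: "Geometric mean titer (GMT) ratios for each HPV genotype will be compared" between the regimens. On the interval it says: "One-sided 90% confidence intervals (adjusted for multiple comparisons) will be constructed for the primary immunogenicity". Its one criterion for declaring non-inferiority is "lower bounds of the multiplicity-adjusted 90% CI for the ratio of antibody GMT greater than 0.67".

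The sample-size paragraph in 7c says that "a sample size of 107 will produce a one-sided 90% confidence limit" lying 0.15 from the mean when the SD is 1.2, and so arrives at an observed ratio of 0.82. Table 1 gives the level for both of its rows as 0.900. On enrolment: "To allow for almost 28% attrition, we will enroll 231 subjects".

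Section 7c does not give the set of types that share the adjustment, the adjustment method, or whether success is judged on HPV16 or on every type.

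**The concern.** A single primary type leaves nothing to adjust for. Either the adjustment does not belong in the primary interval and the decision rule, or HPV16 shares its error rate with other types and 7a does not tell the whole story. The precision statement is written for the first case and the rule for the second.

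At stake is how high the observed HPV16 ratio must be for non-inferiority to be declared. The trial is open-label with historical controls (section 4d), so a rule fixed in advance is one of its main protections. If the scope of the adjustment were settled after the titers were known, a result within a certain range could be made to pass or fail by that choice.

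**Working it through.** **Inputs from section 7c.** Margin 0.67, one-sided level 0.90 (alpha 0.10), SD 1.2, N=107, enrolment 231, attrition 28%. As in the plan's own calculation, the control value is treated as fixed.

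**Step 1: the plan's figure.** Distance d = t(0.90, N−1) × SD / √N.
- SD 1.2: 1.290 × 1.2 / √107 = 0.1496. The plan has 0.150.
- SD 1.0: 1.290 × 1.0 / √107 = 0.1247. The plan has 0.125.
- Ratio needed: 0.67 + 0.15 = 0.82, as stated.

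The smallest N with d ≤ 0.15 is 107. The figures reproduce with no adjustment.

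**Step 2: if k types share the 0.10.** The plan names no method, so Bonferroni is an assumption: d = t(1 − 0.10/k, N−1) × 1.2 / √N. The plan adds the distance to the ratio (0.67 + d). If SD 1.2 is on the ln scale, which is also an assumption, the ratio needed is 0.67 × exp(d).

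| N | k | d | ratio needed, additive | ratio needed, ln |
|---|---|---|---|---|
| 107 | 1 | 0.1496 | 0.820 | 0.778 |
| 107 | 2 | 0.1925 | 0.862 | 0.812 |
| 107 | 9 | 0.2692 | 0.939 | 0.877 |
| 166 | 1 | 0.1198 | 0.790 | 0.755 |
| 166 | 2 | 0.1541 | 0.824 | 0.782 |
| 166 | 9 | 0.2150 | 0.885 | 0.831 |

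The 166 is 231 × 0.72 = 166.3. It is not a target stated in the plan: 107 / 0.72 gives 149, so the plan's N and its enrolment do not follow from each other. Both sizes are therefore shown.

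**Step 3: methods that use correlation between types.** Take nine equally correlated normal statistics and the critical value c for which the largest stays below c with probability 0.90. At assumed correlations of 0.9, 0.7 and 0.5, c is 1.710, 1.966 and 2.109. With 1.2 / √107 = 0.1160:
- d = 0.198, 0.228 and 0.245
- additive ratio needed = 0.87, 0.90 and 0.91

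These lie between 0.82 and 0.94.

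**Step 4: chance that HPV16 passes.** Power = Φ( ln(R/0.67) / (1.2/√N) − z(1 − 0.10/k) ), with N=166, ln scale, 1.2/√166 = 0.0931, and assumed true ratio R.
- R = 0.90: 0.2951 / 0.0931 = 3.169. One type: Φ(3.169 − 1.282) = 0.970. Nine types (Bonferroni): Φ(3.169 − 2.287) = 0.811.
- R = 1.0: 0.4005 / 0.0931 = 4.300. One type: Φ(4.300 − 1.282) = 0.999. Nine types: Φ(4.300 − 2.287) = 0.978.

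**Step 5: when 0.15 and 0.82 do fit the rule.** They fit when HPV16 keeps the full 0.10: tested alone, tested first in a sequence, or with every type required to pass. Under the last rule alpha need not be split, but the joint chance of success falls. By simulation at N=166 on the ln scale, with R = 0.90 for every type, it is 81% to 93% (correlation 0.3 to 0.9). At R = 1.0 it is about 99% or more.

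**The case against.** The strongest reply is that 7a and 7b already settle the matter. HPV16 is the one primary outcome, 7c attaches the interval to the primary immunogenicity, and the sample-size paragraph uses one SD, one distance and one ratio. With a family of one, any adjustment has no effect, and 0.15 and 0.82 follow. This is the most natural reading, and it limits the point. A reader might infer that the plan has no usable decision rule; the documents do not support that, because 7a supplies a primary type. What remains is a contradiction: 7c calls for adjustment twice, once for the primary interval and once in the rule, and that has no purpose for a single test.

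A reader might also infer that N=107 was miscalculated. It was not. The arithmetic is exact for an unadjusted limit, and 0.82 illustrates precision; it is not a second criterion.

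It is fair, too, that the size of the effect rests on assumptions the plan does not make: the method, the number of types, the scale, the evaluable number and a fixed control. Allowing for sampling error in the historical controls would move every threshold. The pilot label does not answer the point, since the trial states a formal non-inferiority criterion.

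**Conclusion.** The inconsistency is real, and the text should be corrected. If the adjustment applies to HPV16, the stated distance and ratio do not describe the decision rule and are too favourable. If it does not apply, the rule should not mention it. The mismatch in the figures therefore depends on HPV16 sharing alpha, which the documents neither establish nor rule out.

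On the plan's own N and additive scale, the distance would be 0.19 or 0.27 and the ratio needed 0.86 or 0.94, for two or nine types by Bonferroni. It would be tempting to take 0.94 as the hurdle the trial really faces. The documents do not support that: it combines an unnamed method, the largest possible family and the smaller of the two sample sizes.

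The practical effect is small if the true ratio is near 1.0 and appreciable near 0.90. It does not call for more participants.

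**What to change.** Make 7c agree with 7a and Table 1 before the antibody results are seen, if they are still pending. Section 7c has the sera shipped in one batch at study end, but the documents do not show whether that has happened.

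The simplest wording states that:
- the primary non-inferiority decision is for HPV16 alone, at the unadjusted one-sided 90% lower limit;
- the other eight types are tested only if HPV16 passes, with a named adjustment over eight at 0.10, such as Bonferroni (whose limits match the decision directly) or Holm.

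The gate has a purpose. If all nine types sit at the margin, HPV16 at 0.10 plus a separate Bonferroni over eight gives a simulated overall error of 0.10 to 0.16 (correlation 0.9 to 0.3; upper bound 0.20). With the gate it stays at 0.10.

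Two alternatives are acceptable. If all nine types must pass, say so and remove the adjustment. If the adjustment is kept for HPV16, name the method and the number of types, and restate 0.15 and 0.82 at the planned N without enrolling more participants.

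The cost is one or two sentences, with no added participants, visits or assays. The simplest version has three drawbacks, which should be acknowledged:
- It makes the HPV16 claim easier than an adjusted limit would.
- HPV16 alone does not by itself support non-inferiority of the 9-valent regimen as section 2 words the aim, so the conclusion should be worded for HPV16, with the other types as secondary.
- Limits for the eight types will be wide: a distance of about 0.26 at N=107 or 0.21 at N=166 with Bonferroni over eight, if SD 1.2 holds for them too.
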